# 6. Plan for reporting UPIRSOs (including Adverse Events) to the IRB

The principal investigator will report the following types of adverse events to the IRB: Any incident, experience or outcome that meets ALL 3 of the following criteria:

- 1. Is unexpected (in terms of nature, specificity, severity, or frequency) given (a) the research procedures described in the protocol-related documents, such as the IRB-approved protocol and informed consent document and (b) the characteristics of the subject population being studied; AND
- 2. Is related or possibly related to participation in the research (possibly related means there is a reasonable possibility that the incident, experience, or outcome may have been caused by the procedures involved in the research); AND
- 3. Suggests that the research places subjects or others at greater risk of harm (including physical, psychological, economic, legal, or social harm) than was previously known or recognized.

Unanticipated Problems Involving Risks to Subjects or Others (UPIRSOs) may be medical or nonmedical in nature, and include – but are not limited to – serious, unexpected, and related adverse events and unanticipated adverse device effects. Please note that adverse events are reportable to the IRB as UPIRSOs **only** if they meet all 3 criteria listed above.

These UPIRSOs/SAEs will be reported to the IRB in accordance with IRB Policy 710, using the appropriate forms found on the website. All related events involving risk but not meeting the *prompt* reporting requirements described in IRB Policy 710 should be reported to the IRB in summary form at the time of continuing review. If appropriate, such summary may be a simple brief statement that events have occurred at the expected frequency and level of severity as previously documented. In lieu of a summary of external events, a current DSMB report can be submitted for research studies that are subject Principal Investigator: [name]

to oversight by a DSMB (or other monitoring entity that is monitoring the study on behalf of an industry sponsor).

7. Plan for reporting adverse events to co-investigators on the study, as appropriate the protocol's research monitor(s), e.g., industrial sponsor, Yale Cancer Center Data and Safety Monitoring Committee (DSMC), Protocol Review Committee (PRC), DSMBs, study sponsors, funding and regulatory agencies, and regulatory and decision-making bodies.

For the current study, the following individuals, funding, and/or regulatory agencies will be notified: (choose those that apply)

X	All Co-Investigators listed on the protocol.
	Yale Cancer Center Data and Safety Monitoring Committee (DSMC)
	National Institutes of Health
	Food and Drug Administration (Physician-Sponsored IND #)
	Medical Research Foundation (Grant)
	Study Sponsor
	Other Data Safety Monitoring Board (DSMB) or Committee (DSMC)

The principal investigator ([name]) will conduct a review of all adverse events upon completion of every study subject. The principal investigator will evaluate the frequency and severity of the adverse events and determine if modifications to the protocol or consent form are required.

Please note: For any study that may be considered high risk, the IRB will be more focused on the safety requirements for the study and a DSMB will likely be required.

#### 4. Confidentiality and Security of Data:

- a) Will private identifiable information about individuals be collected and used? Yes, such data will be collected and recorded during semi-structured interviews with the parent/guardian and the subject. Mood disorders subjects will also be asked to sign a request to obtain/release their specific data they elect to/from Yale and their treatments providers.
- b) How will research data be collected and recorded? *Investigators are reminded that subject identifiers and the means to link subject names and codes with research data should not be stored on unencrypted moveable media, (e.g., laptops, compact discs, jump drives, thumb drives). Identifiers and code keys must be stored in a secure manner, e.g., Yale network servers.*

Biological materials (blood or saliva) for biochemical DNA studies that are collected from individuals are identified by code number rather than by name. For the biochemical and genetic components, the samples that are brought to [name] laboratory for storage and analysis are coded with a letter and number code that does not contain personal identifiers. Accompanying demographic information is limited to age, sex, diagnosis, and ethnicity/race. Scans are also identified by code number with no

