# **Exploratory Aims:**

**Exploratory Aim #4:** Use structural MRI, in combination with study of allelic variation in genes and associated biochemical factors associated with mood disorders (or behaviors that might contribute to or be related to mood disorders), to examine the potential modifying influence of genetic factors on volume abnormalities in children with mood disorders.

*Hypothesis 4:* The presence of the serotonin transporter (SLC6A4) promoter short ("s") allele will be associated with greater AMYG volume increases in children with mood disorders than in HC.

**Exploratory Aim #5:** Use fMRI, in combination with study of allelic variations in genes and associated biochemical factors associated with mood disorders (or behaviors that might contribute to or be related to mood disorders), to examine the potential modifying influence of genetic factors on functional abnormalities in children with mood disorders.

*Hypothesis 5:* The presence of the serotonin transporter (SLC6A4) promoter short ("s") allele will be associated with greater AMYG activation increases in children with mood disorders than in HC

In addition, we will study effects on MRI measures of allelic variation at other strongly favored candidate loci, including, for example, any specific mood disorder risk loci that may be identified over the course of the study. Exploratory analyses will also be performed for the potential modifying influence on AMYG and OFC structure and function of other demographic and clinical factors such as sex, medication exposure, current medications, presence of rapid-cycling, duration of illness, smoking history, family-loading for mood disorders, stressors and socioeconomic status.

**Exploratory Aim #6**: Use MRI, in combination with the study of allele variation in genes and associated biochemical factors and assessments of stress, to examine the potential interaction between genes and stress in influencing the development of AMYG-OFC circuitry and the emergence of disorders of mood and impulse regulation (ADHD and substance use disorders).

*Hypothesis 6A:* Adolescents with high stress exposure, as compared to adolescents with low stress exposure, will show heightened AMYG and ventral striatum response and diminished OFC response to emotional face stimuli.

*Hypothesis 6B*: Abnormal response in the AMYG-ventral striatum-OFC neural system will be associated with impulsive and addictive behaviors.

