#### **Procedures:**

After written informed parental permission is obtained from a parent/guardian of subjects under age 18 years or written informed consent from subjects 18 years old or greater (and written informed assent in subjects <18 years of age), interviews (about 3 - 4 and ½ hours) will be performed at the Yale University School of Medicine, blood draws for genetic and biochemical (to include levels of neurotrophic and immune factors) testing will be performed by a certified phlebotomist at our lab or at the YCCI HRU, and urine toxicology will be performed at either the YCCI HRU or at the Yale University School of Medicine. (Obtaining blood and urine will take about 15 minutes if done at our lab and ½ hour if taken from YCCI HRU which includes the walk to the 10th floor at YCCI HRU and the return walk to Anvlan Center). For the [name] sample, the blood sample may already have been obtained for genetic study, and therefore a blood sample may not need to be redrawn. Results of the urine toxicology will be discussed only with the subject, including if the subject is a minor. Subjects who are unable to give a blood sample but wish to participate in genetic testing may opt to give a saliva sample by spitting into a tube until it is filled to a certain level. The saliva sample process may take up to 20 minutes. Children and their parents will be interviewed separately and together. Scanning will be performed on the 3T system at the Anlyan Center at the Yale University School of Medicine. The scanning session will be 90 minutes long. Further interview information will be collected from the parent during the scanning session in an office on the same level as the scanner in case the child requests their parent during scanning. For follow-up subjects, assessments will follow similar procedures, including pregnancy tests for menstruating females; however, interviews are anticipated to be brief. Diagnosis will be confirmed and clinical changes recorded such as interim episodes, treatment changes and social changes that might affect SES. Genetic testing need not be repeated. We anticipate that total participation will take approximately 4 and ½ - 6 and ½ hours to complete. This time can be divided into different days if preferred by the subject.

The 7T study procedures were the same as for subjects being scanned on the 3T system, except that they were scanned with the 7T MRI system.

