# FMRI Paradigm-Related Behavioral Testing:

Before scanning, subjects will be asked to practice paper and computerized versions of the tasks that will be given to them in the scanner to familiarize them with the neuropsychological stimuli. Accuracy and response time data will be collected. Further testing, e.g. regarding memory for stimuli during scanning may be administered briefly after scanning.

Genotyping and Biochemical Analysis: All blood tubes or saliva samples will be labeled with a code that contains no personal identifying information. DNA extraction and genotyping will be performed in [name] laboratory. DNA will be extracted from 10 ml whole blood or saliva samples using standard methods. Pre-existing subjects who had consented to share their samples and data may have their de-identified information in computer files about their processed samples along with their post processed MRI data sent to the University of Iowa as part of a GWAS. Yale is not receiving information from University of Iowa for this study.

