# **MRI Data Processing:**

Image processing and analysis will be performed at the Yale MR Center on UNIX workstations using standard as well as locally developed software. Data are stripped of all identifying information and assigned a numerical code so that image processors are blind to subject information. Processing will include transformation of brains across subjects into common stereotactic space. Pre-existing subjects who had consented to share their samples and data may have their post processed MRI data along with de-identified information in computer files about their processed samples sent to the University of Iowa as part of a GWAS. Yale is not receiving information from University of Iowa for this study.

- **4. Statistical Considerations:** Describe the statistical analyses that support the study design. This section should include:
  - The number of subjects expected to enter the study.
  - A statement about the statistical power of the study to test the major hypothesis.
  - A summary of the plans for data analysis.

Hypothesis testing will be performed with region of interest measures as the dependent variables, analyzed in mixed models in consultation with a statistician, e.g. with current collaborators such as [name] (EPH) and [name] (GCRC). For example, to test hypothesis #1: diagnosis will be the between subject's variable. Hemisphere (right vs. left) and time (1st scan vs. 2nd scan) will be the within-subject variables and there will be a random subject effect. Repeated measures will be performed over the spatial domain of hemisphere. Total brain volume will be included as a covariate to control for general scaling effects. Terms that are not significant (p>0.05) will be eliminated via a backward stepwise algorithm, with the constraint that the model at each step is hierarchically well-formulated. Least squares means (Is means) and standard errors (SE) will be calculated in the mixed model and plotted to interpret significant interactions.

Whole brain analyses will also be performed to examine for group differences in regions not hypothesized *a priori*. These will be performed with widely available software such as SPM software as well locally developed software.

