# Confidentiality of Data

Biological materials (blood or saliva) for DNA studies collected from individuals are identified by a letter and number code rather than by name. For this genetic component, the samples that are brought to [name] laboratory for storage and analysis are coded with a letter and number code that does not contain personal identifiers. Accompanying demographic information is limited to age, sex, diagnosis,

Principal Investigator: [name]

and ethnicity/race. Scans are also identified by code number. No genotype data are released to subjects or clinicians, or are recorded in the medical record, under any circumstances.

To protect subject confidentiality, subjects will be assigned a letter and number code that will be used when performing data analysis. Paper study documents that contain identifying information will be kept in a locked cabinet in a locked office in the investigator's locked research suite. The letter and number codes with the link to subject identifiers will be stored in a separate computer file on the Yale University fileserver and access will be limited to authorized personnel. This file will be backed-up in encrypted form using Yale University encryption software and will be stored on office desktop computers, as well as CDs stored in a locked file cabinet, in a locked office in the investigator's locked research suite. Some subject information will also be stored on unencrypted electronic databases, but these databases will contain only de-identified data. Laptops and computers will be pass-word protected.

After the study is closed and all data analysis is complete, all identifiers will be removed. The code will continue to be stored in a secure location to verify data should that be necessary. All other personally identifying information will be removed and deleted using the appropriate methods (e.g. zeroing). These records will be destroyed according with policies regarding length of time that research documents need to be retained after protocol completion.

Fate of DNA to be studied and issues of DNA "banking": DNA samples from participants will be retained for future study. This is clearly indicated in the informed consent. A subject or the parent/guardian of a minor subject may request that we destroy the code linking the identifiers of the subject with their DNA sample, so that the sample would only be studied anonymously from that point forward.

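### Diagnosis is sent with coded blood and saliva samples to the laboratory that analyses them, and nothing in the plan keeps assay staff blind to it, although image processors are stated to be blind

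*Combined protocol and SAP*

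**What the plan says.** Section VII, item 4 (Confidentiality and Security of Data), part b, covers the biochemical and the genetic components together. It states that "the samples that are brought to [name] laboratory for storage and analysis are coded with a letter and number code", and then: "Accompanying demographic information is limited to age, sex, diagnosis, and ethnicity/race". Section VII, item 2 (Confidentiality of Data) says the same for the genetic component: "Accompanying demographic information is limited to age, sex, diagnosis", followed by ethnicity or race.

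The Genotyping and Biochemical Analysis paragraph in Section III says of the containers: "All blood tubes or saliva samples will be labeled with a code that contains no personal identifying information". It adds: "DNA extraction and genotyping will be performed in [name] laboratory".

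For imaging, MRI Data Processing in Section III gives an explicit measurement safeguard: "Data are stripped of all identifying information and assigned a numerical code so that image processors are blind to subject information".

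One cohort may differ. Under Procedures in Section III, for that sample "the blood sample may already have been obtained for genetic study, and therefore a blood sample may not need to be redrawn". The plan does not say what information travelled with that blood.

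**The concern.** An assay can be run from the code alone. Once diagnosis is also in the laboratory, every step that needs judgement can vary with it: which samples share a run, which readings are repeated or dropped, and how an unclear genotype call is settled. An error that differs between cases and controls shows up as a group difference, and it does not shrink as the sample grows. Biochemical levels are more exposed than genotype calls, which leave less room for judgement.

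The analyses at stake compare groups directly on a laboratory measurement. The Statement of Purpose sets a long-term goal of identifying loci and alleles that influence vulnerability to mood disorders, and it covers neurotrophic and immune factors linked to those disorders. The plan already treats blinding as worthwhile for image processing and has no counterpart for the assays.

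**Working it through.** The plan states no figure on this point, so there is none to reproduce. The check has three parts.

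**1. The texts side by side**

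| Step | What is masked | Is diagnosis withheld? |
|---|---|---|
| Tube label (Section III) | Personal identity | The label is a code; diagnosis is not said to be on it |
| Transfer to laboratory (Section VII, items 2 and 4b) | Personal identity | No, diagnosis is listed as accompanying the samples |
| Genotyping and assays (Section III) | Nothing stated | Nothing stated |
| Image processing (Section III) | Identity and subject information | Yes, processors are stated to be blind |

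The plan does not describe masking of assay staff, locking of results before diagnosis is merged, or mixing of cases and controls across runs.

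**2. Direct case-control comparisons (illustration only)**

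Inputs from the plan: 396 mood-disorder and 300 healthy participants (Section II, item 5), and 50 per group (Section III, Power). Assumptions: all of them give samples, there is no true difference, and case readings are shifted by δ SD.

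For a two-sided 5% t test, the noncentrality is δ × √(n₁n₂/(n₁+n₂)). The root is √(396×300/696) = 13.06 for the larger groups and √(50×50/100) = 5 for the smaller.

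| δ (SD) | Noncentrality, 396 vs 300 | False-positive rate | Noncentrality, 50 vs 50 | False-positive rate |
|---|---|---|---|---|
| 0.05 | 0.65 | 10.0% | 0.25 | 5.7% |
| 0.1 | 1.31 | 25.7% | 0.50 | 7.9% |
| 0.2 | 2.61 | 74.2% | 1.00 | 16.8% |

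For carrier frequency, assume that 10% of non-carriers are miscalled as carriers in cases only, so the apparent difference is 0.10 × (1 − p). A true carrier rate p of 0.50 gives 0.55 against 0.50. With a standard error of about 0.038, the two-proportion test is falsely positive 25.8% of the time at 396 against 300. With p = 0.65 the comparison is 0.685 against 0.65 and the rate is 16.4%.

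**3. Diagnosis-by-genotype tests on imaging (Hypotheses 4 and 5)**

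Here the outcome is an image measure processed blind. If genotype has no true effect, the outcome is unrelated to the recorded genotype within each diagnosis group, whatever the miscall rate, so the expected interaction is zero.

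If genotype has the same true effect in both groups, say 0.5 SD with a carrier rate of 0.60, recorded carriers among cases are 0.60 + 0.10 × 0.40 = 0.64. True carriers make up 0.60/0.64 = 0.9375 of them. The case effect becomes 0.5 × 0.9375 = 0.469 against 0.5 in controls. The interaction bias is −0.031, which runs against the hypotheses.

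Simulation (4,000 runs per setting, regression with a diagnosis × marker term, two-sided 5%) gave these false-positive rates for the interaction:

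| Assumed error in cases | True marker effect | 396 vs 300 | 50 vs 50 |
|---|---|---|---|
| 10% of non-carriers miscalled | 0 | 4.9% | 4.9% |
| 10% of non-carriers miscalled | 0.5 SD | 5.9% | 4.8% |
| Level shifted by 0.2 SD | 0 to 0.5 SD per SD of marker | 5.5–6.0% | 4.9% |

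These stay at about the nominal level.

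**The case against.** The transfer sentences are confidentiality statements. They cap what may accompany a sample and do not describe how assays are run. A reader might infer that the measurements are made with case or control status in view. The documents do not support that: tubes carry only a code, and the plan does not say who in the laboratory sees the accompanying information. This stands. The text shows that the laboratory receives diagnosis and that no masking is stated, and it shows no more than that.

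A reader might also take the statement to cover every sample, or take all imaging measurement to be blind. Neither is stated. One cohort's blood may have been drawn beforehand, and blinding is given for image processors, not for scan acquisition.

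The most tempting further step is to say that the genetic hypotheses as a whole are compromised. They are not. Hypotheses 4 and 5 have imaging outcomes, and part 3 of the working shows that the assumed errors leave their tests close to nominal. Hypotheses 6A and 6C group by stress exposure, which is not among the items sent to the laboratory, and 6B relates neural response to behaviour. No numbered hypothesis tests a raw case-control difference in biomarker level or allele frequency.

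The illustration also uses assumed shifts and overall enrolment. Participation in parts is optional (Section VI, item 6; Section VIII, item 2), so the number giving samples is unknown. This stands too.

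Last, the laboratory may need diagnosis if its analysis includes association testing. That affects when diagnosis is released. It is no reason to send it before the measurements are fixed.

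**Conclusion.** The point holds in a limited form. Diagnosis is explicitly listed among the items that go with coded samples to the analysing laboratory, and nothing in the plan keeps assay staff blind to it. This is a stated transfer that can be changed, and not merely a silence.

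The risk falls on direct case-control comparisons of biomarker level or allele frequency, and mainly on biochemical levels. The rates of 10% to 74% for levels and 16% to 26% for carrier frequency show how sensitive such comparisons would be at 396 against 300. They rest on assumed errors and full sampling, and they are not evidence that bias has occurred.

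The finding for Hypotheses 4 and 5 assumes that the laboratory error depends on diagnosis and not on the imaging result. The plan lists no imaging result among the items sent with samples.

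Priority is low: primary Aims 1 to 3 are imaging comparisons, and the aims that use laboratory data are exploratory.

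**What to change.** - In Section VII, items 2 and 4b, remove diagnosis from the information that accompanies samples.
- Have the study office hold diagnosis under the code and give the laboratory a code-only run order that mixes cases and controls across runs.
- State that the laboratory returns genotypes and levels with repeats and failures flagged, that these are then locked, and that diagnosis is released for association analysis only after that.

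The cost is two wording changes, a short statement on locking and a run-order list. The small downside is that any quality check or analysis by the laboratory that needs diagnosis waits until after lock. Sample collection continues and DNA is kept indefinitely, so future assays would benefit.
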